#### **Comparison to Licensed Seasonal Influenza Vaccine**

Immunogenicity results from samples collected in this study will be compared to those from banked samples from a previous study of licensed seasonal vaccine in a similar subject population using a 2-sample comparison of means or nonparametric tests as indicated.

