#### **Immunogenicity**

Immunology analyses will be conducted using the Intent-to-treat (ITT) and Per-protocol (PP) Populations with primary conclusions drawn from the PP Population. Analyses based on the ITT Population will be undertaken and presented only if >5% of subjects in any 1 dose group were excluded from the PP Population. No imputation for missing data will be performed. Data will be transformed as appropriate prior to analysis.

Baseline is defined as the sample collected prior to IP administration on Day 1.

The primary variable of interest for assessment of humoral immune response to the NasoVAX antigen is homologous HAI antibody titer. The following HAI immunogenicity measures and their 95% CIs will be summarized by dose group:

- GMT at baseline and postvaccination on Days 4, 8, 15, 29, 91, and 181
- GMR on Days 4, 8, 15, 29, 91, and 181 (analysis of GMR will be performed using analysis of covariance [ANCOVA] with baseline titer as a covariate)
- SPR on Days 4, 8, 15, 29, 91, and 181
- SCR on Days 4, 8, 15, 29, 91, and 181

Humoral immune response as measured by microneutralization in serum will be summarized by GMT at baseline and postvaccination on Day 29 and responder rate (the proportion of subjects with 2-fold and 4-fold rise since baseline) (95% CI) on Day 29.

Cellular responses (ELISpot SFUs to influenza HA peptides) will be summarized by geometric mean at baseline and postvaccination on Day 8 and responder rate on Day 8.

Humoral immune response to nonrepresented influenza strain antigens (antibody level measured by HAI and microneutralization in serum) against each strain tested will be summarized by GMT at baseline and postvaccination on Day 29; GMR postvaccination on Day 29; and responder rate (the proportion of subjects with 2-fold and 4-fold rise since baseline) on Day 29.

For the effect of predose Ad5 serum antibody levels on immunogenicity of NasoVAX on Day 29, analysis will be performed using ANCOVA, with baseline Ad5 titer as a covariate.

Immunogenicity results from samples collected in this study will be compared to those from banked samples from a previous study of licensed seasonal vaccine in a similar subject population using a 2-sample comparison of means or nonparametric tests as indicated.

05 October 2017 Confidential Page 13 of 66

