# **3 STUDY OBJECTIVES AND ENDPOINTS**

OBJECTIVES	ENDPOINTS			
Primary Objective				
• To describe the safety profile of NasoVAX in healthy adults when administered by intranasal spray at a single dose of 1×10  , 1×10  , or 1×10  vp	
 
Reactogenicity: counts and percentages of subject with local events (nasal irritation, sneezing, nasal congestion, cough, sore throat, change in smell, change in taste, change in vision, eye pain) and systemic events (headache, fatigue, muscle ache, nausea, vomiting, diarrhea, chills, fever) for 14 days after vaccination
 
AEs: counts and percentages of subjects with AE from Day 1 to Day 29; MAEs, SAEs, NCIs from Day 1 to Day 181
 
			
Secondary Objective				
• To evaluate the humoral immune response to NasoVAX when administered by intranasal spray at a single dose of 1×10  , 1×10  , or 1×10  vp	
 
Antibody level measured by HAI in serum:         
 
GMT: the antilog of the mean of the log-transformed titers
 
GMR: the ratio of postvaccination and prevaccination GMTs within the same dose group
 
SPR: the percentage of subjects with a HAI titer ≥ 1:40
 
SCR: the percentage of subjects with either a baseline HAI titer < 1:10 and a postvaccination titer ≥ 1:40 (which is 4 times the assay lower limit of quantitation), or a baseline HAI titer ≥ 1:10 and a 4-fold increase in postvaccination HAI titer relative to baseline
 
 
 
Antibody level measured by microneutralization in serum:         
 
GMT
 
Responder rate: the proportion of subjects with 2-fold and 4-fold rise since baseline
 
 
 
			

OBJECTIVES	ENDPOINTS			
Exploratory Objectives				
• To evaluate the cellular immune response to NasoVAX when administered by intranasal spray at a single dose of 1×10  , 1×10  , or 1×10  vp	
 
SFUs to HA peptides measured by enzyme-linke ELISpot in PBMCs:
 
Geometric mean SFUs
 
Responder rate
 
			
• To evaluate the mucosal immune response NasoVAX when administered by intranasal spray at a single dose of 1×10  , 1×10  , or 1×10  vp	
 
IgA antibody level measured by ELISA:
 
GMT
 
GMR
 
			

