To evaluate the humoral immune response against nonrepresented influenza strains after NasoVAX administration	
 
Antibody level measured by HAI and microneutralization in serum against each strain tested:         
 
GMT
 
GMR
 
Responder rate: the number and percentage of subjects with 2-fold and 4-fold rise since baseline
 
 
 
			
To evaluate the effect of predose Ad5 serum antibody levels on the immunogenicity of NasoVAX	
 
Predose Ad5 antibody GMT measured by microneutralization in serum
 
Day 29 GMR and responder rate from antibody level measured by HAI in serum
 
			
To compare immunogenicity results to those obtained from banked samples from a previous study of licensed seasonal vaccine in a similar subject population	
 
Antibody level measured by HAI in serum:         
 
GMT
 
GMR
 
SPR
 
SCR
 
 
 
Antibody level measured by microneutralization in serum:         
 
GMT
 
Responder rate
 
 
 
SFUs to hemagglutinin peptides measured by ELISpot in PBMCs:         
 
Geometric mean SFUs
 
Responder rate
 
 
 
			
	
 
IgA antibody level measured by ELISA:
 
GMT
 
GMR
 
			

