**Study Total Target** 

Total

- Occurrence of 2 Grade 3 AEs in the same organ system
- Occurrence of the same Grade 3 laboratory abnormality in 2 or more subjects

Each subject will record reactogenicity (local events, systemic events, and oral temperature) and whether any medication or treatment was used for the symptom(s) in a diary daily for 14 days after the NasoVAX/placebo dose. Each subject will be contacted by telephone on Day 2 for safety assessment and review of the diary. Subjects will return to the investigational site on Days 4, 8, 15, 29, 91, and 181 for safety and immunogenicity assessments. At each visit, the subject will also be asked about the interim medical history and use of any medications.

A serum sample will be collected from each subject for evaluation of influenza HAI assay against A/California/04/2009 predose on Day 1 on Days 4, 8, 15, 29, 91, and 181; Ad5 antibody, microneutralization assay against both A/California/04/2009(H1N1) and nonrepresented strains,

05 October 2017 Confidential Page 22 of 66

and HAI against nonrepresented strains will also be evaluated at Days 1 and 29. A whole blood sample will be collected from each subject and processed to isolate PBMCs for evaluation of T-cell responses by ELISpot predose on Day 1 and on Day 8.

A nasopharyngeal swab sample will be collected from each subject at Screening and on Days 4, 8, 15, 29, and 91 to measure concentration of the Ad5 vector for assessment of vaccine vector shedding by quantitative polymerase chain reaction (qPCR) assay. Once a negative result is obtained, later samples may not be tested. ELISA for measurement of IgA will also be performed on the swab samples from Screening and Day 29 for evaluation of mucosal immune response.

Banked samples from a previous study of licensed seasonal vaccine in a similar subject population will be analyzed alongside samples collected in this study.

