- 18. Immunocompromised individuals, including those who have used corticosteroids (including intranasal steroids), alkylating drugs, antimetabolites, radiation, immune-modulating biologics, or other immunomodulating therapies within 90 days before Day 1 or those who plan use during the study period
- 19. Use of statin medication within 30 days before Day 1 (see list in Section 6.8.1)
- 20. Receipt of intranasal medications (including over-the-counter medications) within 30 days before Day 1
- 21. Receipt of any IP within 30 days before Day 1
- 22. Receipt of any vaccine within 30 days before Day 1
- 23. Receipt of intranasal vaccine within 90 days before Day 1
- 24. Receipt of any influenza vaccine within 6 months before Day 1
- 25. Any change in medication for a chronic medical condition within 30 days before Day 1
- 26. Past regular use or current use of intranasal illicit drugs
- 27. Smokers, including smoking of any type (eg, cigarettes, electronic cigarettes, marijuana). Prior smokers must have quit smoking at least 30 days before Day 1.
- 28. Any medical, psychiatric, or social condition or occupational or other responsibility that in the judgment of the Investigator would interfere with or serve as a contraindication to protocol adherence, assessment of safety (including reactogenicity), or a subject's ability to give informed consent

05 October 2017 Confidential Page 27 of 66

[figure not shown]

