## 12.8.1 Secondary Endpoints (Humoral Immune Response)

The primary variable of interest for assessment of humoral immune response to the NasoVAX antigen is homologous HAI antibody titer. The following HAI immunogenicity measures and their 95% CIs will be summarized by dose group:

- GMT at baseline and postvaccination on Days 4, 8, 15, 29, 91, and 181
- GMR on Days 4, 8, 15, 29, 91, and 181 (analysis of GMR will be performed using analysis of covariance [ANCOVA] with baseline titer as a covariate)
- SPR on Days 4, 8, 15, 29, 91, and 181
- SCR on Days 4, 8, 15, 29, 91, and 181

05 October 2017 Confidential Page 47 of 66

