#### Effect of Predose Adenovirus Serotype 5 Serum Antibody Levels on Immunogenicity

For the effect of predose Ad5 serum antibody levels on immunogenicity of NasoVAX on Day 29, analysis will be performed using ANCOVA, with baseline Ad5 titer as a covariate.

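### The non-randomised comparison with banked licensed-vaccine samples names only unadjusted tests; baseline-adjusted and fold-rise HAI estimates should be reported together

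*Protocol*

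**What the plan says.** Section 3 lists as an exploratory objective: "To compare immunogenicity results to those obtained from banked samples from a previous study of licensed seasonal vaccine in a similar subject population". Its HAI endpoints are GMT, GMR, SPR and SCR; microneutralization, ELISpot and IgA endpoints follow.

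The method appears in Section 12.8.2 and, in the same terms, in the Synopsis: "Immunogenicity results from samples collected in this study will be compared to those from banked samples from a previous study of licensed seasonal vaccine", "using a 2-sample comparison of means or nonparametric tests as indicated". No covariate, matching or stratification is named.

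Two safeguards are stated. The earlier population is described as similar, and the banked samples "will be analyzed alongside samples collected in this study" (Section 4.1).

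Within the study, Section 12.8.1 treats HAI GMR differently: "analysis of GMR will be performed using analysis of covariance [ANCOVA] with baseline titer as a covariate". For the effect of pre-existing Ad5 antibody, Section 12.8.2 says "analysis will be performed using ANCOVA, with baseline Ad5 titer as a covariate" and names no other term. Section 12.8.1 lists GMT at baseline and after vaccination, but SPR only after vaccination.

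**The concern.** The comparator comes from another study, so randomisation does not balance prior influenza immunity. Running the samples side by side limits assay-run differences, not differences between the people sampled. Eligibility excludes "Receipt of any influenza vaccine within 6 months before Day 1" (Section 5.2) but puts no limit on baseline HAI titre, and the protocol does not say what the earlier study required.

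Baseline imbalance is therefore least controlled in this comparison, yet the protocol names baseline adjustment only for the within-study GMR. If the studies start from different titres, the listed GMT and GMR comparisons can point in opposite directions even when the vaccines perform equally, and a reader would have no stated basis for reconciling them.

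In the Ad5 analysis, omitting dose group and baseline HAI would cost precision. It could also bias the Ad5 slope if Ad5 titre is related to either.

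**Working it through.** The protocol states no figure for this comparison, so there is none to reproduce.

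**Inputs.** From the document: 15 NasoVAX recipients per dose and 45 in total (Table 1). Assumed: log2 baseline SD 1.5, residual SD 1.2, 30 banked subjects, two-sided 5% tests, no true vaccine difference, and a banked baseline higher by d log2 units. Ratios are NasoVAX over banked; b is the slope of post-vaccination on baseline log titre.

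**Formulas.** Two models are possible, and the documents do not show which holds.

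- Common line, y = 2 + b·x + e: GMT ratio 2^(−b·d), GMR ratio 2^((1−b)·d), ANCOVA ratio 1.
- Own means (each study regresses to its own mean m), y = 2 + m + b·(x − m) + e: GMT ratio 2^(−d), GMR ratio 1, ANCOVA ratio 2^(−(1−b)·d).

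For b = 0.5 and d = 1 (2-fold), the common line gives 2^(−0.5) = 0.71, 2^(0.5) = 1.41 and 1.00. Own means gives 2^(−1) = 0.50, 1.00 and 2^(−0.5) = 0.71.

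**Results**, 10,000 simulated trials per scenario; each cell is GMT / GMR / ANCOVA:

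| Baseline gap | Slope | Model | Ratios | False positives |
|---|---|---|---|---|
| none | 0.5 | common | 1.00 / 1.00 / 1.00 | 5 / 5 / 5% |
| 1.4-fold | 0.5 | common | 0.84 / 1.19 / 1.00 | 9 / 9 / 6% |
| 2-fold | 0.5 | common | 0.71 / 1.41 / 1.00 | 19 / 19 / 5% |
| 4-fold | 0.5 | common | 0.50 / 2.00 / 1.00 | 59 / 59 / 6% |
| 1.4-fold | 0.5 | own | 0.71 / 1.00 / 0.84 | 20 / 5 / 10% |
| 2-fold | 0.5 | own | 0.50 / 1.00 / 0.71 | 60 / 5 / 23% |
| 4-fold | 0.5 | own | 0.25 / 1.00 / 0.50 | 99 / 5 / 58% |
| 2-fold | 0.3 | common | 0.81 / 1.62 / 1.00 | 11 / 28 / 5% |
| 2-fold | 0.3 | own | 0.50 / 1.00 / 0.62 | 68 / 5 / 40% |
| 2-fold | 0.8 | common | 0.57 / 1.15 / 1.00 | 30 / 8 / 5% |
| 2-fold | 0.8 | own | 0.50 / 1.00 / 0.87 | 45 / 5 / 8% |

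Hand check of the 2-fold common-line GMT row: the SD of post-vaccination titre is √(0.25 × 2.25 + 1.44) = 1.415 and the SE is 1.415 × √(1/15 + 1/30) = 0.447. Then 0.5/0.447 = 1.12 and Φ(1.12 − 1.96) ≈ 0.20, in line with the simulated 19%.

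In both models the GMR ratio divided by the ANCOVA ratio is 2^((1−b)·d). The gap between the two estimates therefore shows how much the choice matters, but not which assumption is true.

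**Ad5 model.** Assumed: 45 recipients, fold-rise outcome, no true Ad5 effect, Ad5 SD 1.5, b = 0.5, 4,000 trials. With Ad5 as the only term, the slope bias is (b − 1) times the Ad5–HAI correlation: 0, −0.10 and −0.20 at correlations 0, 0.2 and 0.4, with false positives of 5%, 11% and 29%. If mean Ad5 rises 0.5 log2 per cohort and response rises 0.5 or 1 log2 per cohort, false positives are 7% and 14%. With dose group and baseline HAI added they are about 5%.

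With no correlation, the SE of the Ad5 slope falls from 0.144 to 0.126 (12%), 0.150 to 0.127 (15%) and 0.166 to 0.126 (24%) at dose effects of 0, 0.5 and 1 log2 per cohort. At correlation 0.4 with no dose effect it falls only from 0.141 to 0.138 (2%).

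**Day 1 SPR.** The exact binomial chance that two groups of 15 differ by at least 3 subjects (20 points) on Day 1 is 12%, 25%, 32%, 36% and 32% for a true baseline SPR of 10%, 20%, 30%, 50% and 70%.

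**The case against.** Section 12 calls itself brief and promises a detailed SAP, which may well add adjustment. That disposes of most complaints about missing detail. It does not fully dispose of this one, because the protocol names a method for the banked comparison and the method is unadjusted.

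The comparison is not blind to baseline. GMR is a change from baseline, and SCR counts a "4-fold increase in postvaccination HAI titer relative to baseline" among subjects with a measurable starting titre. The ANCOVA stated for GMR in Section 12.8.1 might also be read as carrying over. This stands in part: under the own-means model the unadjusted fold rise is unbiased. It does not rescue the unadjusted post-vaccination GMT comparison.

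The strongest objection concerns the remedy. A reader might infer that ANCOVA should become the lead method. The documents do not support that: under own means, ANCOVA has 23% false positives at a 2-fold gap while fold rise has 5%. In a non-randomised comparison neither can be preferred from what the protocol gives.

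A reader might also infer that the comparison is biased as planned. Nothing shows that baselines differ, and with equal baselines the bias is zero. The protocol attaches no significance level or decision rule to this comparison, so the false-positive rates only illustrate the size of the problem.

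On Ad5, ANCOVA ordinarily includes a group factor, so dose group may already be intended, and Section 12.8.1 may imply baseline HAI when the outcome is GMR. Dose group alone returns the 7% and 14% figures to about 5%. What remains is that the section does not say so.

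On SPR, baseline GMT and SCR already show part of the picture, and no between-group SPR test is specified.

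**Conclusion.** The point holds in a limited form. The only method named for the non-randomised banked comparison is unadjusted. If baseline HAI titres differ and post-vaccination titre depends on baseline, the unadjusted GMT comparison is biased under both models. Under a common line with slope between 0 and 1, GMT and GMR err in opposite directions. At an assumed 2-fold gap and slope 0.5, the GMT ratio is 0.71 or 0.50 depending on the model, with no true difference; at a 1.4-fold gap on a common line, false positives are about 9%. These sizes rest on assumed SDs, slope, banked sample size and baseline gap.

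The Ad5 point is a cheap gain in precision and protection against confounding, if the extra terms are not already intended. The Day 1 SPR point is presentational.

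Severity is minor. The banked and Ad5 analyses are exploratory, the SPR summary is secondary and descriptive, and the primary safety objective is unaffected.

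**What to change.** In Section 12.8.2 and the Synopsis, for the HAI GMT/GMR comparison with banked samples:

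- Report baseline GMT for both studies.
- Present two co-reported estimates with 95% CIs: an ANCOVA of log post-vaccination titre on log baseline titre, and the unadjusted log fold rise.
- State that ANCOVA assumes a baseline relation common to both studies, and that fold rise assumes no regression toward a common mean.
- State that the comparison is non-randomised and descriptive, and that other between-study differences and the SPR, SCR, microneutralization, ELISpot and IgA comparisons are not addressed by this adjustment.
- Do not rely on the unadjusted post-vaccination GMT comparison alone.

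In the Ad5 paragraph of Section 12.8.2 and the Synopsis, state that the model for log HAI response in NasoVAX recipients includes dose group and log baseline HAI titre. This does not cover the binary responder rate listed for that objective. Optionally, add Day 1 to the SPR time points in Section 12.8.1 and the Synopsis.

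The cost is wording, a few model terms and possibly one table column. No new sampling is needed: Day 1 serum is collected, and the GMR and SCR listed for the banked comparison already require banked pre-vaccination titres. The Ad5 model uses three more degrees of freedom (two for dose group, one for baseline HAI) among 45 subjects.

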#### 12.9 Sample Size and Power

The sample size for this study was selected as adequate and reasonable for an initial review of the safety and immunogenicity profile of the NasoVAX at doses to be well tolerated by young adults, rather than for statistical power. The sample size will permit initial estimates of reactogenicity. Given a total of 45 subjects receiving NasoVAX, the study will have an 80% probability of detecting at least 1 AE which occurs at a rate of 3.6%. If no SAEs are observed among the 45 subjects who receive NasoVAX, an approximation to the 1-sided upper bound of the 90% CI on the rate of SAE occurrence would be 5%.

05 October 2017 Confidential Page 48 of 66

#### 12.10 Interim and Final Analyses

One interim analysis of humoral immunogenicity data and safety data (including summaries of AE, reactogenicity, concomitant medications and vaccines, vital signs, ECG, and laboratory data and listing of any viral culture results) will be conducted when all data through the Day 29 visit are available, monitored, and confirmed by the Investigator for all subjects. The purpose of this review is to plan future studies and adjust the clinical development plan accordingly.

An unblinded team composed only of members not otherwise involved in the study, will perform the interim analysis. All other study personnel including Investigators and investigational site staff and Sponsor staff and contractors will remain blinded to individual treatment assignments until database lock for final analysis.

Safety and immunogenicity analyses from the interim review may be presented in an interim statistical report drafted by the Sponsor. Data therein will be used to support development and planning of future studies, and may be submitted to the Center for Biologics Evaluation and Research and other Regulatory Authorities as needed.

The final CSR will include all study data through the end of study.

05 October 2017 Confidential Page 49 of 66

## 13 ETHICAL, LEGAL, AND ADMINISTRATIVE ISSUES

The procedures set out in this study protocol, pertaining to the conduct, evaluation, and documentation of this study, are designed to ensure that the Sponsor and the Investigator abide by Good Clinical Practice (GCP) as described in International Council for Harmonisation (ICH) Guideline E6 and with all relevant laws. Compliance with these regulations also constitutes compliance with the ethical principles that have their origins in the Declaration of Helsinki.

#### 13.1 Institutional Review Board Approval

The protocol, the ICF, any advertisement, or any other written information provided to the subject will be reviewed and approved by the Institutional Review Board (IRB). The Sponsor will supply relevant material for the Investigator to submit to the IRB for the study's review and approval.

The IRB will be informed of amendments to the study protocol, ICF, advertisement, or written information provided to the subject. Such amendments may not be implemented until approval by the IRB except when necessary to eliminate immediate hazards to the subjects.

The IRB will be provided with reports at the interval required (not to exceed 1 year) and a report after the completion or discontinuation of the Investigator's participation in the study.

#### 13.2 Informed Consent

The Investigator (or designee) will explain the nature of the study to each subject. The subjects will be informed that participation is voluntary and that they can withdraw from the study at any time. After the study has been fully explained, each subject will provide written informed consent to study participation. The informed consent process will be documented by the use of a written ICF approved by the IRB and signed by the subject before protocol-specific procedures are performed.

A copy of the ICF will be given to the subject, and the original ICF will be maintained with the subject's study records.

## 13.3 Biological Samples

Biological samples collected for this study will become the property of the Sponsor and may be used for future research conducted by or on behalf of the Sponsor or its affiliates, partners, or collaborators. No identifiable personal information will be associated with these blood samples. Any samples remaining 15 years after the end of the study will be destroyed.

Subjects who provide informed consent for the study will be informed that any residual samples may be retained for as yet undetermined additional testing. These tests may include human leukocyte antigen typing of the PBMC samples. Subjects will be asked explicitly to consent for such sample retention and potential future genetic research on their blood samples.

A subject who is unwilling to have blood samples stored for future use can consent to participate in this study without having blood samples stored for future testing. In this case, the subject's blood samples will be destroyed after all the tests specified for this study have been concluded.

05 October 2017 Confidential Page 50 of 66

A subject can withdraw consent for sample retention at any time, in which case the samples will be destroyed and no further testing will take place. To initiate the sample destruction process, the Investigator must notify the Sponsor about the withdrawal of consent for the storage of samples for future use and request sample destruction.

